8.2 Responsibility for Analyses/In-House Blinding

The statistical analysis of the data obtained from this study will be the responsibility of the Clinical Biostatistics department of the SPONSOR.

The Sponsor will generate the randomized allocation schedule(s) for study treatment assignment for this protocol, and the randomization will be implemented in IVRS.

Although the trial is open label, analyses or summaries generated by randomized treatment assignment, actual treatment received, and/or PD-L1 biomarker status will be limited and documented. Further documentation will be provided in the sSAP. In addition, the CAC blinded central review will be performed without knowledge of treatment group assignment.

The ORR and PFS analyses, described in Section 8.6.1, occur prior to the final OS analysis. Treatment-level results at the ORR and PFS analysis and interim OS will be provided by the external unblinded statistician to the DMC. Key enrollment metrics and study data will also be monitored by the external unblinded statistician to inform the timing of the PFS and interim OS analyses, as needed. Limited additional SPONSOR personnel may be unblinded to the treatment level and/or PD-L1 biomarker results of the first ORR and PFS analyses, if required, in order to act on the recommendations of the DMC or facilitate regulatory filing. The extent to which individuals are unblinded with respect to results of interim analyses will be documented by the unblinded statistician.

The DMC will serve as the primary reviewer of the unblinded results of the ORR and PFS analysis and interim OS and will make recommendations for discontinuation of the study or modification to an executive oversight committee of the SPONSOR. Depending on the recommendation of the DMC, the Sponsor may prepare a regulatory submission. If the DMC recommends modifications to the design of the protocol or discontinuation of the study, this executive oversight committee may be unblinded to results at the treatment level in order to act on these recommendations. Additional logistical details, revisions to the above plan and data monitoring guidance will be provided in the DMC Charter.

8.3 Hypotheses/Estimation

Objectives and hypotheses of the study are stated in Section 3.0

8.4 Analysis Endpoints

8.4.1 Efficacy Endpoints

Primary

Progression-free survival (PFS) – the International Myeloma Working Group response criteria (IMWG 2011) by CAC blinded **central review**

PFS is defined as the time from randomization to the first documented disease progression per IMWG 2011 based on CAC blinded central review or death due to any cause, whichever occurs first. See Section 8.6.1 for definition of censoring.

Overall Survival (OS)

OS is defined as the time from randomization to death due to any cause. Subjects without documented death at the time of the final analysis will be censored at the date of the last follow-up.

Secondary

Overall Response Rate (ORR) – the International Myeloma Working Group response criteria (IMWG 2011) by CAC **blinded central review**.

ORR is defined as the proportion of the subjects in the analysis population who achieved at least a partial response according to the IMWG 2011.

Duration of Response (DOR) – the International Myeloma Working Group response criteria (IMWG 2011) by CAC **blinded central review**.

For subjects who demonstrated at least a partial response, response duration is defined as the time from first documented evidence of at least a partial response until disease progression or death. Response duration for subjects who have not progressed or died at the time of analysis will be censored at the date of their last assessment.

Disease Control Rate (DCR) - the International Myeloma Working Group response criteria (IMWG 2011) by CAC **blinded central review**.

Disease control rate (DCR) is defined as the percentage of subjects who have achieved confirmed CR, VGPR, PR, MR or have demonstrated SD for at least 12 weeks prior to any evidence of progression.

Second Progression-Free Survival (PFS2) - the time from randomization to subsequent disease progression after initiation of new anti-cancer therapy, or death from any cause, whichever occurs first, **based on Investigator assessment**.

8.4.2 Safety Endpoints

Safety measurements are described in Section 7.0.

8.5 ANALYSIS POPULATIONS

8.5.1 Efficacy Analysis Populations

The Intention-to-Treat (ITT) population will serve as the population for primary efficacy analysis. All randomized subjects will be included in this population. Subjects will be included in the treatment group to which they are randomized. Details on the approach to handling missing data are provided in Section 8.6 Statistical Methods.

8.5.2 Safety Analysis Populations

The All Subjects as Treated (ASaT) population will be used for the analysis of safety data in this study. The ASaT population consists of all randomized subjects who received at least one dose of study treatment. Subjects will be included in the treatment group corresponding to the study treatment they actually received for the analysis of safety data using the ASaT population. For most subjects this will be the treatment group to which they are randomized. Subjects who take incorrect study treatment for the entire treatment period will be included in the treatment group corresponding to the study treatment actually received. Any subject who receives the incorrect study medication for one cycle but receives the correct treatment for all other cycles will be analyzed according to the correct treatment group and a narrative will be provided for any events that occur during the cycle for which the subject is incorrectly dosed.

At least one laboratory or vital sign measurement obtained subsequent to at least one dose of study treatment is required for inclusion in the analysis of each specific parameter. To assess change from baseline, a baseline measurement is also required.

Details on the approach to handling missing data for safety analyses are provided in Section 8.6 Statistical Methods.

8.6 STATISTICAL METHODS

8.6.1 Statistical Methods for Efficacy Analyses

This section describes the statistical methods that address the primary and secondary objectives. Methods related to exploratory objectives and exploratory endpoints will be described in the supplemental statistical analysis plan (sSAP), this includes the ePRO data described in 7.1.2.9. In addition, a separate SAP will describe the analysis of Pharmacokinetic (PK) data described in Section 7.1.3.2

Efficacy results that will be deemed to be statistically significant after consideration of the Type I error control strategy are described in Section 8.8, Multiplicity and Section 8.7 Interim Analysis. Nominal p-values will be provided for other efficacy analyses, but should be interpreted with caution due to potential issues of multiplicity.

Progression-free Survival (PFS)

The non-parametric Kaplan-Meier method will be used to estimate the PFS curve in each treatment group. The treatment difference in PFS will be assessed by the stratified log-rank test. A stratified Cox proportional hazards model with Efron's method of tie handling will be used to assess the magnitude of the treatment difference (ie, hazard ratio) between the treatment arms. The hazard ratio and its 95% confidence interval from the stratified Cox model with Efron's method of tie handling and with a single treatment covariate will be reported. Disease status and number of previous treatments will be used as the stratification factors in both the stratified log-rank test and the stratified Cox model.

Since disease progression is assessed periodically, PD can occur any time in the time interval between the last assessment where PD was not documented and the assessment when PD is documented. For the primary analysis, for the subjects who have PD, the true date of disease progression will be approximated by the date of the first assessment at which PD is objectively documented per IMWG 2011, regardless of discontinuation of study drug. Death is always considered as a confirmed PD event. Subjects without documented PD/death will be censored at the last disease assessment date.

In order to evaluate the robustness of the primary endpoint PFS per IMWG 2011 criteria by CAC blinded central review, two sensitivity analyses will be performed with a different set of censoring rules. The first sensitivity analysis is the same as the primary analysis except that it censors at the last disease assessment without PD when PD or death is documented after more than one missed disease assessment. The second sensitivity analysis is the same as the primary analysis except that it considers discontinuation of treatment or initiation of an anticancer treatment subsequent to discontinuation of study-specified treatments, whichever occurs later, to be a PD event for subjects without documented PD or death. The censoring rules for primary and sensitivity analyses are summarized in [Table 14](#) below. In case there is an imbalance between the treatment groups on disease assessment schedules or censoring patterns, additional PFS sensitivity analyses may be performed: 1. A PFS analysis using time to scheduled disease assessment visit from randomization as opposed to actual disease assessment time and 2) Finkelstein (1986)'s likelihood-based score test [55] for interval-censored data, which modifies the Cox proportional hazards model for interval censored data, will be used as a supportive analysis for the PFS endpoint. The interval will be constructed so

that the left endpoint is the date of the last disease assessment without documented PD and the right endpoint is the date of documented PD or death, whichever occurs earlier.

Table 14 Censoring rules for Primary and Sensitivity Analyses of PFS

Situation	Primary Analysis	Sensitivity Analysis 1	Sensitivity Analysis 2
No PD and no death; new anticancer treatment is not initiated	Censored at last disease assessment	Censored at last disease assessment	Censored at last disease assessment if still on study therapy; progressed at treatment discontinuation otherwise
No PD and no death; new anticancer treatment is initiated	Censored at last disease assessment before new anticancer treatment	Censored at last disease assessment before new anticancer treatment	Progressed at date of new anticancer treatment
PD or death documented after ≤ 1 missed disease assessment	Progressed at date of documented PD or death	Progressed at date of documented PD or death	Progressed at date of documented PD or death
PD or death documented after ≥ 2 missed disease assessments	Progressed at date of documented PD or death	Censored at last disease assessment prior to the ≥ 2 missed disease assessment	Progressed at date of documented PD or death

The proportional hazards assumption of the Cox model will be examined using both graphical and analytical methods for the PFS analysis. The log[-log] of the survival function vs. time for PFS will be plotted for each treatment arm. If the curves are not parallel, indicating that hazards are not proportional, supportive analyses may be conducted to account for the possible non-proportional hazards effect associated with immunotherapies, for example, using Restricted Mean Survival Time (RMST) method [56], parametric method [57] etc. Details will be described in supplemental SAP.

Overall Survival (OS)

The non-parametric Kaplan-Meier method will be used to estimate the survival curves. The treatment difference in survival will be assessed by the stratified log-rank test. A stratified Cox proportional hazards model with Efron's method of tie handling will be used to assess the magnitude of the treatment difference (ie, the hazard ratio). The hazard ratio and its 95% confidence interval from the stratified Cox model with a single treatment covariate will be reported. Disease status and number of prior treatments will be used as the stratification factors in both the stratified log-rank test and the stratified Cox model.

Exploratory analyses to adjust for the effect of subsequent lines of therapy on OS may be performed based on recognized methods, eg, the Rank Preserving Structural Failure Time (RPSFT) model proposed by Robins and Tsiatis (1989) [58], two stage model, etc. The choice of the method will be based on an examination of the appropriateness of the data to the assumptions required by the method. Other sensitivity analyses described for the PFS endpoint will be applied to OS endpoint as appropriate. Further details of sensitivity analyses will be described in supplemental SAP.

Overall Response Rate (ORR)

The stratified Miettinen and Nurminen's method based on sample size weighting will be used for comparison of the ORR between the treatment groups. A 95% confidence interval for the difference in response rates between the active arms and the standard therapy arm will be provided. Disease status and number of prior treatments will be used as the stratification factors in the analysis.

Duration of Response (DOR)

If sample size permits, response duration will be summarized descriptively using Kaplan-Meier medians and quartiles, results permitting. Only the subset of subjects who show at least a partial response will be included in this analysis. Additional details on the censoring rules for DOR will be provided in the supplemental SAP.

Disease Control Rate (DCR)

The stratified Miettinen and Nurminen will be used for comparison of the DCR between the treatment groups, using sample size weighting. A 95% confidence interval for the difference in disease control rates between the active arms and the standard therapy arm will be provided. Disease status and number of prior treatments will be used as the stratification factors in the analysis.

Second Progression-free Survival (PFS2)

The non-parametric Kaplan-Meier method will be used to estimate the PFS2 curves. The treatment difference in PFS2 will be assessed by the stratified log-rank test. A stratified Cox proportional hazards model with Efron's method of tie handling will be used to assess the magnitude of the treatment difference (ie, the hazard ratio). The hazard ratio and its 95% confidence interval from the stratified Cox model with a single treatment covariate will be reported. Disease status and number of prior treatments will be used as the stratification factors in both the stratified log-rank test and the stratified Cox model. Further details of PFS2 analyses will be described in supplemental SAP.

[Table 15](#) summarizes the primary analysis approach for primary and secondary efficacy endpoints. Sensitivity analysis methods are described above for each endpoint.

Table 15 Analysis Strategy for Key Efficacy Endpoints

Endpoint/Variable (Description, Time Point)	Statistical Method†	Analysis Population	Missing Data Approach
Primary Endpoint			
PFS per IMWG 2011 by CAC blinded central review	Testing: Stratified Log-rank test. Estimation: Stratified Cox model with Efron's tie handling method	ITT	
 • Primary censoring rule • Sensitivity analysis 1 • Sensitivity analysis 2 (More details in Table 14)
OS	Testing: Stratified Log-rank test Estimation: Stratified Cox model with Efron's tie handling method	ITT	
 • Censored at last date known alive
Secondary endpoints			
ORR per IMWG 2011 by CAC blinded central review	Stratified Miettinen and Nurminen method	ITT	Subjects with missing data are considered non-responders
DOR per IMWG 2011 by CAC blinded central review	Summary statistics using Kaplan-Meier method	All responders in ITT	Censored at last assessment date if responding at the time of analysis
DCR per IMWG 2011 by CAC blinded central review	Stratified Miettinen and Nurminen method	ITT	Subjects with missing data are considered as disease not under control
PFS2 per investigator assessment	Testing: Stratified Log-rank test. Estimation: Stratified Cox model with Efron's tie handling method	ITT	Details to be provided in sSAP
† Statistical models are described in further detail in the text. Disease status and lines of prior treatments will be used as the stratification factors in the stratified log-rank test, stratified Miettinen and Nurminen's test and the stratified Cox model.			

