Table 17	Decision Guidance at Each Efficacy Analysis	105
Table 18	Product Descriptions	108

LIST OF FIGURES

Figure 1 Trial Diagram 19
Figure 2 Consistency of Observed Concentration Data in KEYNOTE-013 Subjects
with Hematologic Malignancies Receiving 10 mg/kg Q2W pembrolizumab
with Predicted Pharmacokinetic Profile for this Dose Regimen (Preliminary
Results)..... 26
Figure 3 Multiplicity Strategy..... 106

DOCUMENT HISTORY

Document	Date of Issue	Overall Rationale
MK-3475-183-06	04-JUN-2020	To discontinue data collection following the database lock for the final analysis, as all participants remaining on study are in survival follow-up.
MK-3475-183-05	12-APR-2018	To allow flexibility in the entire follow-up period and enable more frequent follow-up visits if necessary.
MK-3475-183-04	05-OCT-2017	To communicate that the study was placed by the US FDA on clinical hold.
MK-3475-183-03	07-DEC-2016	To clarify eligibility, treatment after discontinuation of one treatment is discontinued, and trial assessments. To reinforce compliance after PD. To add survival sweep language.
MK-3475-183-02	20-MAY-2016	Clarification to ensure patients who may have a history of pneumonitis are excluded from the study (when applicable).
MK-3475-183-01	10-MAR-2016	To reinforce and adhere to the pregnancy prevention plan and risk minimization program established for the use of pomalidomide. To update IMWG 2006 criteria with IMWG 2011 criteria. To update endpoints per agency request. To update Exploratory Biomarker Research per guidance of the I-O BMx Science Forum

Document	Date of Issue	Overall Rationale
MK-3475-183-00	22-JUL-2015	Original

SUMMARY OF CHANGES

PRIMARY REASON(S) FOR THIS AMENDMENT:

Section Number (s)	Section Title(s)	Description of Change (s)	Rationale
1.0	Trial Summary	Updated duration of survival follow-up to 12 months following discontinuation visit.	To allow for early closure of the study.
2.1	Trial Design	Updated follow-up after stem cell transplant (SCT) to provide for completion of follow-up at the end of the trial.	Follow-up post allogenic-SCT will end when the trial closes. Survival follow-up will continue for at least 12 months following the last discontinuation visit.
5.10	Beginning and End of Trial	Updated criteria for end of the trial to include Sponsor decision to close.	To broaden the criteria for ending the trial.

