7.1.5.5 Efficacy Follow-up Visits

Subjects who discontinue trial treatment for a reason other than confirmed disease progression will move into the Efficacy Follow-Up Phase to monitor disease status and should be assessed every 4 weeks (\pm 7 days) until (1) the start of new anti-cancer treatment, (2) documented disease progression, (3) death, (4) withdraw of consent or (5) the end of the trial, whichever occurs first. The Sponsor may request survival status to be assessed at additional time points during the course of the study (not to exceed approximately 12 weeks). Every effort should be made to collect information regarding disease response assessment in the follow-up period. Prior to discontinuing patients from therapy, consult with Sponsor and submit the Treatment Termination & Disease Assessment Termination Form.

NOTE: For both groups, if either pembrolizumab, pomalidomide, or low dose dexamethasone is discontinued due to unacceptable toxicity, subjects can continue to receive study treatment with the remaining study drugs without discontinuing from study.

Information regarding post-study anti-myeloma treatment will be collected if new treatment is initiated.

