7.1.5.5.1 Survival Follow-up

Once a subject experiences confirmed disease progression or starts a new anti-myeloma therapy, the subject moves into the Survival Follow-up phase and should be contacted approximately every 12 weeks for at least 12 months following their discontinuation visit for assessment of survival status until death, withdrawal of consent, or the end of the study, whichever occurs first.

Survival status data may be requested more frequently than every 12 weeks. The Sponsor may request these additional data at time points such as prior to data cleaning, an external Data Monitoring Committee (eDMC) safety review, and/or efficacy interim analyses. All subjects who are in the Survival Follow-Up Phase and not known to have died prior to the request for these additional survival data will be contacted at that time.

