8.0 STATISTICAL ANALYSIS PLAN

This section outlines the statistical analysis strategy and procedures for the study. If, after the study has begun, changes are made to primary and/or key secondary hypotheses, or the statistical methods related to those hypotheses, then the protocol will be amended (consistent with ICH Guideline E-9). Changes to exploratory or other non-confirmatory analyses made after the protocol has been finalized, but prior to the conduct of any analysis, will be documented in a supplemental SAP (sSAP) and referenced in the Clinical Study Report (CSR) for the study. A separate PK analysis plan as well as biomarker analysis plan will be provided. Post hoc exploratory analyses will be clearly identified in the CSR. The PRO analysis plan will also be included in the sSAP.

On 03-JUL-2017, the US FDA placed KN183, KN185 and cohort 1 of KN023 on clinical hold based on safety data from KN183 and KN185 presented to the DMC. The FDA determined that the risks of pembrolizumab plus pomalidomide or lenalidomide outweighed any potential benefit for patients with multiple myeloma. Based on this decision, the treatment phase of KN183 and KN185 is closed effective immediately. All subjects must stop study treatment, complete the Discontinuation Visit and move into the long-term safety and survival follow-up per protocol.

Due to the current status of the study the statistical analysis of this section may be modified and will be reported in the CSR.

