Multiplicity	
The family-wise type I error rate for this study is strongly controlled at 2.5% (one-sided) for the hypothesis testing of ORR, PFS and OS. The multiplicity strategy will follow the graphical approach of Maurer and Bretz (2013) as described in Section 8.8, with 0.5%, 1.5% and 0.5% alpha allocated to the ORR, PFS and OS hypothesis, respectively.
 
For the OS hypothesis, a Hwang-Shih-DeCani alpha-spending function with the gamma parameter (-6) is constructed to implement group sequential boundaries that control the type I error rate. Further details of the interim analysis strategy can be found in Section 8.7.1

Sample Size and Power	
The planned sample size is approximately 300 subjects. The primary endpoints of the study are PFS and OS. For PFS, based on 236 events, the study has ~90.6% power to detect a hazard ratio of 0.635 (pembrolizumab in combination with SOC vs. SOC) at alpha = 1.5% (one-sided). For OS, based on 182 events, the study has ~ 80.5% power to detect a hazard ratio of 0.600 (pembrolizumab in combination with SOC vs. SOC) at alpha = 0.5% (one-sided). For ORR based on the first 210 randomized patients followed for two cycles of treatment or have discontinued earlier, the study has 88.7% power to detect a 25 percentage point increase for pembrolizumab in combination with SOC vs SOC at alpha = 0.5% (one-sided)

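### If PFS is cut after the 03-JUL-2017 clinical hold, Sensitivity Analysis 2 as written counts hold-stopped subjects with no documented progression or death as progressions

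*Combined protocol and SAP*

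**What the plan says.** Section 8.6.1 presents SA2 as one of two checks on the robustness of primary PFS. For subjects with no documented progression or death, Table 14 gives SA2 two outcomes:

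- Row 1, no new anticancer treatment: "Censored at last disease assessment if still on study therapy; progressed at treatment discontinuation otherwise".
- Row 2, new anticancer treatment started: "Progressed at date of new anticancer treatment".

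The text above the table agrees, taking the later of the two dates as the event. Rows 3 and 4 put documented progression or death at its own date. The primary analysis and Sensitivity Analysis 1 censor the row 1 and row 2 subjects.

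Section 8.0 reports the hold and its effect: "All subjects must stop study treatment, complete the Discontinuation Visit and move into the long-term safety and survival follow-up per protocol". It adds: "Due to the current status of the study the statistical analysis of this section may be modified and will be reported in the CSR". No replacement rule for SA2 follows, and Table 14 has no exception by reason for stopping.

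Section 7.1.5.5 keeps subjects who stop for reasons other than progression under four-weekly disease assessment "until (1) the start of new anti-cancer treatment, (2) documented disease progression, (3) death", or until consent is withdrawn or the trial ends. Section 7.1.5.5.1 then continues: "Once a subject experiences confirmed disease progression or starts a new anti-myeloma therapy, the subject moves into the Survival Follow-up phase". Section 8.6.1 counts any death as a PFS event.

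**The concern.** SA2 uses treatment discontinuation as a stand-in for unrecorded progression. That is reasonable when subjects stop because they are failing. It is not reasonable when a regulator stops everyone on one date. After the hold, no compliant subject is still on study therapy, so the censoring half of row 1 is empty. Subjects who were progression-free when treatment ended become events for a reason unrelated to their disease.

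These added events fall in proportion to the number still event-free in each arm. Whichever arm is doing better receives more of them, and the contrast shrinks. A gap between SA2 and primary PFS could then be read as fragility of the result when it only reflects the hold. In a trial stopped for safety, dilution of a possible harm matters as much as dilution of a benefit.

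**Working it through.** **Inputs from Section 8.9.** 300 subjects, 1:1; uniform accrual over 14 months; exponential PFS with control median 4 months; hazard ratio 0.635; dropout 5% per year. Monthly hazards: control ln2/4 = 0.1733; Arm A 0.635 × 0.1733 = 0.1100; dropout d = −ln(0.95)/12 = 0.00427.

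**The plan's own figures.** Schoenfeld power for 236 events at one-sided 1.5% is 90.6% (stated ~90.6%). Expected events at month 20 are 235.9 (stated ~236). Expected events at months 14, 18 and 23 are 164.8, 218.7 and 254.1.

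**Assumptions not in the documents.** The hold month is not stated. The original protocol is dated 22-JUL-2015, so I take month 14 to 23. All progression-free subjects are taken as on therapy at the hold; if 20% had already stopped, the hold-related counts fall by 20%. Where new therapy is modelled, its start is exponential with median 3 months after the hold (rate n = ln2/3 = 0.231). Deaths after new therapy follow the Section 8.9 OS hazards: control ln2/12.7 = 0.0546, Arm A 0.6 × 0.0546 = 0.0327.

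**Step 1: progression-free at the hold.** With k = hazard + d, each arm has N = (150/14) × [exp(−k(T−14)) − exp(−kT)]/k. At T = 14 this is 74.8 in Arm A and 55.3 in Arm B, 130.1 in all. At T = 18 it is 47.4 + 27.2 = 74.5. At T = 23 it is 26.7 + 11.2 = 37.9.

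**Step 2: row 1 after F further months without new therapy.** The count is N × [q + (d/k)(1 − q)], with q = exp(−kF). For T = 14 and F = 6: Arm A 39.1, Arm B 19.9, total 59.0. For T = 18 and F = 2: 38.0 + 19.3 = 57.3. For T = 14 and F = 24: 9.5.

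**Step 3: row 2 with deaths recorded.** Let k′ = k + n and m = the OS hazard. The count is N × n/(k′ − m) × [exp(−mF) − exp(−k′F)]. For T = 14 and F = 24: Arm A 25.2, Arm B 9.7, total 34.9. Setting m = 0 (deaths ignored) gives 81.3. At F = 35, roughly the date of amendment 06, the count with deaths is about 23. Row 1 adds 1.5 at F = 24, so 36.4 remain; simulation gives up to 38.

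**Step 4: which cases fit the planned trigger.** Section 8.7.1 analyses PFS at about 236 events, expected near month 20. A hold at month 20 or later comes after that trigger, so those cases need a departure from Section 8.7.1. A hold at month 14 with six months' further assessment and no new therapy reaches 236 at month 20. With new therapy, primary events at month 20 are 164.8 at the hold + 42.3 later progressions + 10.9 deaths after new therapy = 218. At month 26 they are 164.8 + 46.7 + 25.4 = 237.

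**Step 5: hazard ratios** (simulation, unstratified Cox model, true hazard ratio 0.635).

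| Hold month | Cut month | New therapy | Artificial events | Primary HR | SA2 HR |
|---|---|---|---|---|---|
| 14 | 20 | none | 59 | 0.63–0.64 | 0.79 |
| 14 | 20 | median 3 months, deaths counted | 77 | 0.63 | 0.75 |
| 14 | 26 | median 3 months, deaths counted | 58 | 0.64–0.65 | 0.75 |
| 18 | 20 | none, or median 3 months | 57–61 | 0.63–0.64 | 0.70–0.71 |
| 14 | 38 | median 3 months, deaths counted | 35–38 | 0.68 | 0.76 |

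For a month-14 hold without new therapy, SA2 is 0.77 with no further assessment or with twelve months, and 0.69 with 24 months. With a true hazard ratio of 1, SA2 stays at 0.99 to 1.01. With a true hazard ratio of 1.5 and a month-14 hold, SA2 is 1.33 with no further assessment. At 24 months it is 1.48 without new therapy, or 1.41 with it when later deaths are ignored.

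**The case against.** The strongest reply is that the premise is not in the documents. No PFS cut date is given. The Document History entry of 04-JUN-2020 reads "To discontinue data collection following the database lock for the final analysis, as all participants remaining on study are in survival follow-up". A reader might infer from it that PFS was cut after the hold. It concerns the final analysis, however, and Section 8.7.1 lists a final OS analysis later than the final PFS analysis. A post-hold PFS cut is plausible, not shown. This stands, and the point is conditional for that reason.

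A reader might also infer that SA2 was actually run this way. The documents do not support that. Section 8.0 allows modification and sends changes to non-confirmatory analyses to the supplemental SAP, which is not among the documents. The permission supplies no rule, though, so Table 14 as it stands still gives the wrong result.

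A third tempting reading is that the new-therapy row never empties, because disease assessment ends when new therapy starts. It does shrink: survival follow-up continues and deaths count as events. Counts that ignore those deaths (about 83 for a month-14 hold, 25 for month 23) are upper limits.

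Row 1 may be nearly empty by a late cut, since survival follow-up is normally entered through progression or new therapy. The documents leave this unsettled: Section 7.1.5.5 continues disease assessment, while the hold text sends everyone to long-term safety and survival follow-up.

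Finally, SA2 carries no alpha. Section 8.1 describes the split "with 0.5%, 1.5% and 0.5% alpha allocated to the ORR, PFS and OS hypothesis, respectively". That limits how much the point matters.

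**Conclusion.** Wrong as written, conditional on a PFS cut after 03-JUL-2017. In that case SA2 turns every hold-stopped subject without documented progression or death into an event, at the stop date or at the start of new therapy.

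Under the Section 8.9 assumptions, and in cases close to the planned 236 events, the SA2 hazard ratio is about 0.77 to 0.79 for an assumed hold at month 14. It is about 0.75 with new therapy at an assumed median of 3 months, and about 0.70 to 0.71 for a hold at month 18 cut at month 20. The primary hazard ratio is about 0.63 (up to 0.65 for the later cut). With 24 months' follow-up after a month-14 hold, new therapy and deaths counted, the figures are about 0.76 against 0.68.

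The pull is toward 1 in either direction and does not reverse the effect. With long follow-up and few new-therapy starts it is small. The primary PFS analysis, Sensitivity Analysis 1 and type I error are unaffected, so this is a minor correction to a supportive analysis. The reading of the rule is firm; the sizes rest on an assumed hold month and assumed new-therapy timing.

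**What to change.** Add one line to the SA2 column of Table 14, or to the supplemental SAP: a discontinuation required by the 03-JUL-2017 hold, and new anticancer therapy begun after such a discontinuation without progression, is not a PFS event. Those subjects follow the primary censoring rule, and documented progression or death still counts. Keep the existing rule for all other discontinuations.

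Identify hold stops by the recorded reason for discontinuation, which Section 8.6.3.1 shows is collected. The documents do not say whether that reason singles out the hold. If it does not, use discontinuation on or after the hold date with no other recorded cause.

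State the PFS data cut date. If it precedes the hold, no change is needed. The cost is one line of text and one programming flag; no new data are required.
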